6.7. Intervention after the End of the Study

No continued access is planned after completion of this study, as additional efficacy would be needed to demonstrate continued access criteria.

7. Discontinuation of Study Intervention and Participant Discontinuation/Withdrawal

These sections describe reasons for a participant's

- permanent or temporary discontinuation of study drug, or
- discontinuation (withdrawal) from the study.

Discontinuation of specific sites or of the trial as a whole are handled as part of regulatory, ethical, and trial oversight considerations in Section 10.1. Appendix 1.

7.1. Discontinuation of Study Intervention

In rare instances, it may be necessary for a participant to permanently discontinue study intervention. If the IV infusion is permanently stopped, the participant will remain in the study for follow-up and further evaluations as described in the SoA.

7.2. Participant Discontinuation/Withdrawal from the Study

A participant may withdraw from the study

- at any time at his/her own request
- at the request of his/her designee (for example, parents or legal guardian)
- at the discretion of the investigator for safety, behavioral, compliance, or administrative reasons
- if the participant becomes pregnant during the study
- if enrollment in any other clinical study involving an investigational product or enrollment in any other type of medical research judged not to be scientifically or medically compatible with this study

See the SoA for data to be collected at the time of study discontinuation and follow-up and for any further evaluations that need to be completed. The participant will be permanently discontinued both from the study intervention and from the study at that time.

If the participant withdraws consent for disclosure of future information, the sponsor may retain and continue to use any data collected before such a withdrawal of consent. If a participant withdraws from the study, they may request destruction of any samples taken and not tested, and the investigator must document this in the site study records.

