- Participants begin a single IV infusion of study intervention, and
- Site completes all safety monitoring and post-infusion sample collection.

Discharge from hospital

Participants discharged from the hospital will complete study procedures outlined in the SoA.

If hospital discharge	Then
Occurs prior to Day 29	participants will be asked to complete the remaining
	study assessments at the timepoints indicated in the
	SoA.
	NOTE: Strategies to manage infection risks and reduce
	the burden of return visits should be considered by
	sites, such as home visits.
Occurs on the same day as a study assessment visit	hospital discharge assessments do not need to be
	repeated if the study assessments occurred within 8
	hours of discharge and there has been no change in
	clinical status.
Does not occur at or prior to day 29	assessments will continue to occur weekly up to Day
	60 or until hospital discharge, whichever is sooner.

Post-treatment follow-up

Post-treatment follow-up assessments will be conducted at Day 60. Strategies to manage infection risks and reduce the burden of return visits should be considered by sites, such as home visits.

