5.2. Exclusion Criteria

Participants are excluded from the study if any of the following criteria apply:

Medical Conditions

- 10. Require invasive mechanical ventilation or anticipated impending need for invasive mechanical ventilation
- 11. Anticipate transfer to another hospital which is not a study site within 5 days of randomization

- 12. Have known allergies to any of the components used in the formulation of the interventions
- 13. Have hemodynamic instability requiring use of pressors within 24 hours of randomization
- 14. Were resident in a nursing home or long-term care facility immediately prior to current hospitalization
- 15. Suspected or proven serious, active bacterial, fungal, viral, or other infection (besides COVID-19) that in the opinion of the investigator could constitute a risk when taking intervention
- 16. Have any co-morbidity requiring surgery within <7 days, or that is considered life-threatening within 29 days
- 17. Have prior history of hepatic impairment, such as
 - a. severe liver cirrhosis Child-Pugh B or worse
 - b. cirrhosis with a history of hepatic encephalopathy
 - c. clinically meaningful ascites requiring ongoing treatment with diuretics and/or paracentesis, or
 - d. history of hepatorenal syndrome.
- 18. Have any serious concomitant systemic disorder that, in the opinion of the investigator, would preclude participation in the study
- 19. Current diagnosis of active malignancy that, in the opinion of the investigator, could constitute a risk when taking investigational product
- 20. Received convalescent COVID-19 plasma treatment prior to enrollment

Diagnostic assessments

- 21. Have an SpO2 <88% while breathing room air at rest. If on supplemental oxygen at the time of screening, use the last time point of measurement on room air up to 48 hours prior
- 22. This criterion was removed
- 23. Have alanine aminotransferase (ALT) or aspartate aminotransferase (AST) >5X upper limit of normal (ULN)
- 24. Have acute kidney disease with an eGFR <30 mL/min/1.73 m² based on the chronic kidney disease epidemiology collaboration equation (CKD-EPI). Chronic kidney disease is allowable, if judged to be stable for the past 3 months, in the opinion of the investigator.

Other Exclusions

- 25. Are pregnant or breast feeding
- 26. Are concurrently enrolled in any other type of medical research judged not to be scientifically or medically compatible with this study
- 27. Are Lilly employees

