6.1. Study Intervention(s) Administered

This is a single dose study.

Intervention Names	LY3819253	Placebo
Туре	Biologic	Not applicable
Dose Formulation	solution	0.9% Sodium chloride solution
Unit Dose Strength(s)	700 mg/vial	Placebo
Planned Dosage Level(s)	Cohort 1: 700 mg Cohort 2: 2800 mg Cohort 3: 7000 mg Optional Cohort 4 may explore lower or equal levels to the max investigated dose, but will not exceed 7000 mg.	Not applicable
Route of Administration	IV infusion	IV infusion
Use	experimental	placebo
IMP and NIMP	IMP	IMP
Sourcing	From Lilly	Commercially available 0.9% sodium chloride solution will be used as a placebo for this study
Packaging and Labeling	Study Intervention will be provided in glass vials and will be labeled appropriately	Commercially available 0.9% sodium chloride solution will be used as a placebo for this study

Abbreviations: IMP = investigational medicinal product; NIMP = non-investigational medicinal product.

This table describes the infusion volume and rate for the planned LY3819253 doses. Cohort 4 instructions will be provided in the pharmacy instructions. Placebo volume and rate will match the LY3819253 dose cohort.

LY3819253 Dose (mg)	Volume (mL)	Start Infusion rate x Time
700	50	100 mL/hr x 30 min
2800	75	100 mL/hr x 45 min
7000	100	100 mL/hr x 60 min

The infusion rate may be reduced as deemed necessary if an infusion reaction is observed.

During the infusion, vital signs will be monitored every 15 minutes as described in the SoA.

After completion of the infusion, participants will be monitored every 30 minutes for 2 hours and then every 1 hour for the next 4 hours.

The site must have resuscitation equipment, emergency drugs and appropriately training staff available during the infusion and for at least 4 hours after the completion of the infusion.

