6.5. Concomitant Therapy

Prior Treatment for Indication

Any prior therapy, such as antivirals, antibiotics, or antimalarials used as treatment prior to signing informed consent should be recorded.

Therapy prior to enrollment with antivirals including lopinavir/ritonavir, remdesivir or other therapeutic agents (e.g. corticosteroids) are permitted.

Convalescent COVID-19 plasma treatment is not allowed prior to enrollment.

Concomitant Therapy

Participants should be treated according to standard of care, even as it evolves, and medications may be part of the treatment paradigm. Therefore, remdesivir may be initiated as standard of care for participants hospitalized with severe disease (if available through the FDA Emergency Use Authorizations) outside of local standard of care per written policies or guidelines.

If the local standard of care per written policies or guidelines (that is, not just an individual clinician decision) includes lopinavir/ritonavir, chloroquine, hydroxychloroquine or other investigational agents, then initiating these during the study is permitted, but may require additional safety monitoring by the site.

Convalescent COVID-19 plasma treatment is not allowed.

Any medication, investigational agent, or vaccine, including over the counter or prescription medicines, vitamins, and/or herbal supplements, or other specific categories of interest that the participant is receiving at the time of enrollment or receives during the study must be recorded along with:

- Reason for use
- Dates of administration including start and end dates
- Dosage information including dose and frequency for concomitant therapy of special interest

Acetaminophen and corticosteroid use are permitted at any time during the study.

Other concomitant medication may be considered on a case-by-case basis by the investigator in consultation with the sponsor if required.

The sponsor should be contacted if there are any questions regarding concomitant or prior therapy.

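### Protocol 7.2 can end study participation when a participant joins another investigational-product study, although after the single Day 1 infusion only follow-up is left to end

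*Protocol*

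**What the plan says.** Protocol 7.2 opens its list of grounds permissively: "A participant may withdraw from the study". One bullet reads "if enrollment in any other clinical study involving an investigational product", and continues to other medical research judged incompatible with this study. The consequence is worded as mandatory: "The participant will be permanently discontinued both from the study intervention and from the study at that time". The section also points to the Schedule of Activities (SoA) for data to be collected at discontinuation and afterwards.

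Three other places in the protocol bear on this:

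- Section 6.1: "This is a single dose study". The infusion lasts 30 to 60 minutes at the planned doses.
- Section 7.1, on a permanently stopped infusion: "the participant will remain in the study for follow-up and further evaluations as described in the SoA".
- Section 5.2, exclusion 26: "Are concurrently enrolled in any other type of medical research judged not to be scientifically or medically compatible with this study".

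Follow-up is meant to run on: "Post-treatment follow-up assessments will be conducted at Day 60" (Protocol 4.1). Under 8.3.1, AEs and SAEs are collected until study participation ends. SAP 10.1 provides listings up to the point of withdrawal. Neither document says how data after joining another study would be analysed.

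**The concern.** A rule that takes a participant off study makes sense when treatment is still being given. Here nothing is left to stop once the infusion ends, so the only effect of applying 7.2 is to end observation. That runs against 7.1, where a participant who did not receive the full infusion is still followed.

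At stake are the primary objective (safety and tolerability), the secondary PK endpoint (Day 29 concentration) and a secondary PD endpoint (viral-load AUC). The dose groups in Cohorts 1-3 have six active participants each, so one avoidable loss is noticeable. If the decision to join another study is related to how the participant is doing, the loss is also informative.

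**Working it through.** **1. The passages side by side**

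| Situation | Rule | Follow-up afterwards |
|---|---|---|
| Infusion permanently stopped (7.1) | Off intervention | Continues per SoA |
| In other research at entry (exclusion 26) | Barred only if judged incompatible | Continues per SoA if enrolled |
| Joins another investigational-product study later (7.2) | Listed as a ground; discontinued from intervention and study | Ends, apart from the items in step 2 |

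Two points in 7.2 are unclear. The list says a participant may withdraw, while the consequence says the participant will be discontinued, so removal could be optional or automatic. The compatibility qualifier reads most naturally as covering only the second kind of research, but it could be read as covering both. On that wider reading 7.2 would be in line with exclusion 26.

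**2. What remains and what is lost**

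Remains:
- The SoA column shared by hospital discharge and early discontinuation covers AEs, vital signs, clinical status, laboratory tests, PK, ADA and swab.
- Reported SAEs are followed to resolution or stabilization (8.3.3).
- Investigators stay responsible for following AEs that are serious, related, or led to discontinuation (8.3).
- Related SAEs that the investigator later learns of are notified (8.3.1).

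Lost:
- New AEs, SAEs and deaths between exit and Day 60 are not actively sought (8.3.1).
- The Day 29 concentration is lost if exit comes before that visit.
- The viral-load AUC is lost as well, because SAP 10.4.2 calculates none when the Day 29 value is missing.
- Replacement, up to 3 per cohort, is tied to 8 participants completing 7 days (9.2), so later exits are not made good.

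**3. The plan's own safety figure**

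Inputs from Protocol 9.2: 6 participants per treatment, prevalence 25%, stated probability above 80%.

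P(at least one event) = 1 − (1 − 0.25)^6 = 1 − 0.178 = 0.822. The stated figure reproduces.

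**4. The same figure with participants lost**

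For an event that would arise only after exit, with no replacement:

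- one of six lost: 1 − 0.75^5 = 76.3%
- two lost: 1 − 0.75^4 = 68.4%
- three lost: 1 − 0.75^3 = 57.8%

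These are worst-case values, because events before exit are still captured. One loss is enough to fall below 80%.

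**5. Is the participant still exposed?**

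Protocol 4.3 projects a half-life of about 19 days. Assuming simple exponential decay, the fraction remaining is 0.5^(days since dose/19):

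- Day 15: 0.5^(14/19) = 60%
- Day 29: 0.5^(28/19) = 36%
- Day 60: 0.5^(59/19) = 12%

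An exit in the first weeks therefore ends active observation while much of the drug is still present.

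**The case against.** The case for leaving 7.2 alone has real force. Stopping an infusion and leaving a study are different things, and the protocol treats them separately. A rule for later events may be stricter than an entry criterion without contradicting it. In a first-in-human study, a second investigational agent can confound attribution of AEs and viral load, and Protocol 4.2 shows concern about confounded safety signals. The permissive opening of 7.2 may mean that nobody is removed automatically. Much safety information also survives exit, as step 2 shows.

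Most of this stands, and it rules out several stronger readings that a reader might infer:

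- **That all later safety data are lost.** They are not. The loss is of new events that are no longer actively sought.
- **That Section 6.5 conflicts with 7.2.** Section 6.5 says of "other investigational agents, then initiating these during the study is permitted", but only where written local standard of care includes them. That is treatment, not enrolment in a trial, and both rules can be followed.
- **That the Day 15 worsening comparison is biased.** If worsening prompts the move to another study, it has already happened. Clinical status is recorded on Days 1, 2, 3, 4, 7, 11 and 15 and at early discontinuation. If the endpoint means any worsening up to Day 15, the event would still be counted. Loss arises mainly if status at Day 15 is meant.

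The objection does not explain why follow-up should end. Confounding by a second agent can be handled by recording that agent and analysing with and without the later data. Data never collected cannot be recovered.

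**Conclusion.** The point holds in a limited form. Applied as written, 7.2 ends active follow-up after dosing is complete, for a reason that does not require it, and its wording leaves sites free to act differently. In a dose group of six, one exit lowers the detection probability for a 25%-prevalence event by about 6 percentage points, from 82.2% to 76.3%. This assumes that the event would occur only after exit and that the participant is not replaced. An exit before Day 29 also costs that participant's Day 29 concentration and viral-load AUC.

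A reader might go further and infer that the rule removes the participants who are deteriorating. That is plausible in hospitalised patients, but no passage shows it, and well or discharged participants could join another study too. The documents give no joining rate, so neither the number of exits nor any difference between arms can be estimated. The loss may be related to outcome; it has not been shown to be. This is a cheap improvement, not a threat to the study's validity.

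**What to change.** **Protocol.** Reconcile 7.2 with 7.1 and exclusion 26. State that joining another study after the infusion does not by itself end SoA follow-up to Day 60, unless consent is withdrawn or the investigator ends participation on another listed ground. Say whether the compatibility qualifier applies to both kinds of research. Record the co-enrolment date and the agent.

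**SAP.** Include data after co-enrolment in the safety and clinical-status analyses, and show a sensitivity analysis censored at the co-enrolment date.

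**Cost.** Wording at the next amendment, one CRF field and one extra analysis. The downside is that later data may be confounded by the second agent; the censored analysis addresses that.

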7.2.1. Discontinuation of Inadvertently Enrolled Participants

If the sponsor or investigator identify a participant who did not meet enrollment criteria and was inadvertently enrolled, then the participant should be discontinued from study treatment unless there are extenuating circumstances that make it medically necessary for the participant to continue study treatment.

If the investigator and the sponsor CRP agree it is medically appropriate to continue, the investigator must obtain documented approval from the sponsor CRP to allow the inadvertently enrolled participant to continue in the study with or without treatment with investigational product.

Safety follow up is as outlined in

- Section 1.3 (Schedule of Activities),
- Section 8.2 (Safety Assessments), and
- Section 8.3 (Adverse Events and Serious Adverse Events).

7.3. Lost to Follow up

A participant will be considered lost to follow-up if, after discharge from the hospital, they do not return for scheduled visits and are unable to be contacted by the study site. Site personnel are expected to make diligent attempts to contact participants who fail to return for a scheduled visit or were otherwise unable to be followed up by the site.

8. Study Assessments and Procedures

Study procedures and their timing are summarized in the SoA (Section 1.3).

Protocol waivers or exemptions are not allowed.

Immediate safety concerns should be discussed with the sponsor immediately upon occurrence or awareness to determine if the participant should continue or discontinue study intervention.

Adherence to the study design requirements, including those specified in the SoA, is essential and required for study conduct.

All screening evaluations must be completed and reviewed to confirm that potential participants meet all eligibility criteria. The investigator will maintain a screening log to record details of all participants screened and to confirm eligibility or record reasons for screening failure, as applicable.

8.1. Efficacy Assessments

This section is not applicable for this study.

8.2. Safety Assessments

8.2.1. Physical Examinations

A complete physical examination will be performed at the screening visit. This examination excludes pelvic, rectal, and breast examinations unless clinically indicated.

A symptom-directed physical examination will be performed at other visits, as specified in the SoA and as clinically indicated.

Investigators should pay special attention to clinical signs related to COVID-19, to ongoing medical conditions and to previous serious illnesses.

8.2.2. Vital Signs

Vital signs will be measured as specified in the SoA and as clinically indicated. Vital signs include

- Body temperature
- Blood pressure
- Pulse rate
- Respiration rate
- Saturation of peripheral oxygen, and
- Supplemental oxygen flow rate, FiO2 if known, and method of delivery, if applicable.

Additional vital signs may be measured during the study if warranted, as determined by the investigator.
8.2.3. Electrocardiograms

A single, local, 12-lead electrocardiogram (ECG) will be obtained as outlined in the SoA using an ECG machine that automatically calculates the heart rate and measures pulse rate, QRS, QT, and corrected QT intervals. Additional ECG readings may occur at investigator discretion.

8.2.4. Clinical Laboratory Assessments

See Section 10.2, Appendix 2 for the list of clinical laboratory tests to be performed and the SoA for the timing and frequency. All protocol-required laboratory assessments, as defined in Appendix 2, must be conducted in accordance with the laboratory manual and the SoA.

The investigator or appropriate designee must review the laboratory report, and record any clinically relevant changes occurring during the study in the AE section of the CRF.

Documentation of the review may be completed according to institution processes or by making an entry in the participants' progress notes (medical record) stating that the laboratory results have been reviewed.

The laboratory reports must be filed with the source documents unless a source document agreement or comparable document cites an electronic location that accommodates the expected retention duration.

If laboratory values from non-protocol specified laboratory assessments performed at the institution's local laboratory require a change in participant management or are considered clinically significant by the investigator (e.g., serious adverse event [SAE] or AE or dose modification), then the results must be recorded in the CRF.

Pregnancy Testing

Women of childbearing potential (WOCBP) must undergo pregnancy testing according to the SoA. Participants who are pregnant will be discontinued from the study (Section 7.2).

8.2.5. Hospitalization events

The date of hospitalization events will be recorded in the CRF and includes when the participant is hospitalized, admitted to the ICU, discharged from the ICU, discharged from the hospital, admitted to an extended care facility, discharged to home.

8.2.6. Procedures of Special Interest

The participants' clinical status and concurrent procedures of special interest will be recorded in the CRF and include limitation on activities due to COVID-19 and requirements for

- ongoing hospital medical care
- supplemental oxygen
- non-invasive ventilation or a high flow oxygen device
- mechanical ventilation
- ECMO
- additional organ support (e.g. pressors, renal replacement), or
- consciousness status using alert, consciousness, verbal, pain, unresponsive scale (ACVPU).

8.2.7. Respiratory Support

Once enrolled in the study, participants may be managed with high-flow nasal cannula, noninvasive positive pressure ventilation or any other form respiratory support as needed per investigator discretion.

8.3. Adverse Events and Serious Adverse Events

AEs will be reported by the participant or, when appropriate, by a caregiver, surrogate, or the participant's legally authorized representative.

The investigator and any qualified designees are responsible for detecting, documenting, and recording events that meet the definition of an AE or SAE and remain responsible for following up AEs that are serious, considered related to the study intervention or study procedures, or that caused the participant to discontinue the study intervention or study.

Discontinuation information is in Section 7.

Detailed AE definitions and procedures are in Section 10.3

AEs and SAEs related to COVID-19 are subject to different reporting requirements detailed in Section 10.3.1.

